	The study is designed as a comparison of two kinds of treatment: Group BipolEP: Bipolar transurethral enucleation of the prostate Group TURP: Bipolar transurethral resection of the prostate
	Two primary endpoints are chosen: (1): IPSS after 12 month [-] (2): Tissue resection [g/min]
	The use of a gate keeping approach makes it unnecessary to adjust the type I error. Primary endpoint (1) will be investigated by a non-inferiority approach (type I error = 5% one-sided), primary endpoint (2) by a superiority approach (type I error = 2.5% one-sided).
	Hypotheses:
	(1): H-0 ₁ : Compared to group TURP, IPSS after 12months in group BipoIEP is higher (non-inferiority range = 3) H-1 ₁ : Compared to group TURP, IPSS after 12months in group BipoIEP is not higher (non-inferiority range = 3)
	(2): H-0 ₂ : Compared to group TURP, tissue resection in group BipolEP is not increased H-1 ₂ : Compared to group TURP, tissue resection in group BipolEP is increased
Statistical	Statistical Methods:
analysis	Group Comparisons:
	Primary Endpoint (1): Data (if appropriate, in logarithmised version) will be checked for normal distribution (Kolmogorov-Smirnov with Lilliefors significance correction, type I error = 10%). Hypotheses (H-0 ₁ , H-1 ₁) will be investigated either by a parametric or by a non-parametric one-sided test of equivalence (equivalence range one-sided = 3; type I error = 5% one-sided).
	Primary Endpoint (2): Data (if appropriate, in logarithmised version) will be checked for normal distribution (Kolmogorov-Smirnov with Lilliefors significance correction, type I error = 10%). Hypotheses will be investigated either by the t-test for independent samples or by the Mann-Whitney U-test (type I error = 2.5% one-sided). Hypotheses (H-0 ₂ , H-1 ₂) will be tested only if H-0 ₁ hypothesis is rejected.
	Further Variables: All other variables will be analysed by usual parametric and non-parametric tests for univariate comparisons of independent samples.
	Two-sided 95% confidence intervals: For selected variables, two-sided 95% confidence intervals will be calculated.
	Type I error adjustment: No adjustment for the type I error will be made. Therefore – apart from hypotheses testing – the results of inferential statistics will be descriptive only.
	Sample Size Justification:

The following scenario was used for the sample size estimation concerning primary endpoint (1):

- Non-inferiority range = 3
- Type I error = 5% one-sided
- Type II error = 10%

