- IPSS after 12 months in both groups (Mw ± SD) = 4 ± 4
- n (group BipolEP) / n (group TURP) = 1 / 1
- Parametric test

The result of the sample size estimation is a requirement of 31 cases per group. Assuming a drop-out rate of 20% and considering the possible need for a non-parametric test a total of 84 inclusions (n=42 / group) are chosen as the sample size of the study.

Analysis Populations:

Intent-to-treat (ITT) population: All subjects at whom the group-specific treatment (TURP, BipoIEP) at least has started will be included in the ITT population. All variables will be analysed.

Per-protocol (PP) population: All subjects without occurrence of any drop-out situation (all valid cases) will be included in the PP population. All variables will be analysed. The PP analysis is paramount.

Handling of Implausible Values and of Missing Values:

Implausible values have to be identified during the data management process in agreement with the clinical investigator. They will be converted into missing values.

Missing Values will be replaced only in the ITT population and only for the two primary endpoints. The replacements will be made according to the worst-case principle (use of the worst assessed value in the study).

Post-hoc Analyses:

Analyses of subgroups and other post-hoc analyses can be performed for cause. However, all statistical results will be only descriptive.

Interim Analyses:

A priori no interim analysis is intended.

Presentation of the Results (Descriptive Analysis, Graphs etc.):

Categorical variables will be presented using counts and percentages. Variables measured on ordinal scales will be presented using counts and percentages (where appropriate) or minimum, 25%-percentile, median, 75%-percentile and maximum and number of patients (where appropriate). Continuous variables will be presented using minimum, 25%-percentile, arithmetic mean, median, 75%-percentile, maximum, standard deviation and number of patients.

All results will be presented in the form of tables, selected results additionally in the form of graphs (bar charts, boxplots).

Allcation

For the allocation of treatment to subjects the minimization method will be used (manual see accompanying documents).

	Strata:
	prostate 60 to 80 ml / more than 80 ml
	catheterized / non-catheterized
	The minimization procedure will be applied centrally (by the coordinating centre).

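### The set labelled ITT is a treated set, so no planned population analyses all allocated men in their allocated arm

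*Combined protocol and SAP*

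**What the plan says.** The Analysis Populations section of the combined protocol and SAP defines two sets and no others.

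- ITT: subjects in whom the treatment specific to their group, with TURP and BipolEP both named in a parenthesis, "at least has started will be included in the ITT population".
- Per-protocol (PP): "All subjects without occurrence of any drop-out situation (all valid cases) will be included in the PP population". The events that count as drop-out are not listed.
- Priority: "The PP analysis is paramount".

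The section on missing values adds: "Missing Values will be replaced only in the ITT population and only for the two primary endpoints". The substitute is the worst value observed in the study.

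Allocation is by central minimisation. Its timing relative to surgery is not stated. Nothing in the document covers withdrawal between allocation and surgery, a change to the other operation, or the arm in which a switched man is counted.

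**The concern.** An intention-to-treat set protects the randomised comparison because membership is fixed at allocation. Here membership depends on something that happens afterwards, and the operator must know the arm before starting. Loss from the set can therefore depend on both arm and prognosis.

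PP selects after allocation by design. That is a common lead analysis for non-inferiority, but it needs a companion set free of the same selection. Both planned sets can lose men before surgery, so agreement between them would say nothing about that loss. Any resulting bias in endpoint (1), IPSS at 12 months, also carries into endpoint (2), tissue resection in g/min, because the second is tested only if the first succeeds.

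**Working it through.** **1. The plan's own figure.** The sample-size section gives: margin 3, one-sided alpha 5%, power 90%, mean 4 and SD 4 in both groups. Then n = 2 × [4 × (1.645 + 1.282) / 3]² = 30.45, rounded up to 31 per group, as stated. The step to 42 also reproduces if the non-parametric allowance is taken as 3/π (my assumption; the plan gives none): 31 / 0.955 rounds up to 33, and 33 / 0.8 rounds up to 42. The sample size is not in dispute.

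**2. Who is in which set.**

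| Man after allocation | ITT as written | PP as written |
|---|---|---|
| Allocated operation started, then converted or abandoned | In | Depends on the undefined drop-out term |
| Withdraws, no operation | Out on any reading | Out, if withdrawal is a drop-out |
| Given the other operation from the outset | Out on the literal reading; in if either operation counts, arm unstated | Undefined; could be a valid case |

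Replacement of missing values cannot bring back the second man, because he is not in the set to which it applies.

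**3. Illustrative size.** The documents give no rates, so what follows is assumption. Take 34 evaluable men per arm (42 × 0.8 = 33.6) and SD 4. Suppose k BipolEP men, and none in the TURP arm, are left out, and that they would have scored 8 points (2 SD) higher. The hidden arm difference is k × 8 / 34. The chance of declaring non-inferiority comes from 20,000 simulated trials (pooled t test, margin 3, one-sided 5%).

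| k | Hidden difference | Declared, men left out | Declared, men kept as allocated |
|---|---|---|---|
| 2 | 0.47 | 0.91 | 0.80 |
| 4 | 0.94 | 0.90 | 0.61 |
| 6 | 1.41 | 0.89 | 0.41 |

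With a milder shift of 4 points the pairs are 0.92 and 0.88, 0.91 and 0.81, 0.90 and 0.74. With all 42 per arm and a shift of 8 they are 0.96 and 0.89, 0.96 and 0.78, 0.95 and 0.60. If the men left out do not differ in outcome, the hidden difference is 0.

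**4. The opposite risk.** Suppose BipolEP is truly 3 points worse, exactly at the margin, and k of 34 BipolEP men receive TURP and score at the TURP mean. Kept as allocated, they pull the arms together: the expected difference falls to 3 × (34 − k) / 34, which is 2.82, 2.65 and 2.47 for k = 2, 4 and 6. Simulated false declarations of non-inferiority are about 7%, 10% and 13%, against about 5% when these men are left out.

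**The case against.** The defence has four good points.

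- The clause keeps every man whose allocated operation begins, including those converted or abandoned, and worst-case replacement penalises loss to follow-up after surgery. Only the interval between allocation and the start of surgery is exposed, and it may be short. This stands and limits the reach of the point.
- A reader might infer that switched men vanish from every analysis. The text does not establish that. The parenthesis naming both operations can be read as either one having started, and the PP definition turns on an undefined term, so a switched man with a 12-month IPSS could be a valid case. What is certain is that his handling is unspecified.
- A reader might also infer that the definition would produce a false claim of non-inferiority. The scenarios in step 3 do not show this. Their true differences lie inside the margin of 3, so the lower probabilities are reduced power for a correct conclusion. Reaching 3 points at a shift of 8 would need 3 × 34 / 8 = 12.75, so about 13 of 34 men, all lost from one arm.
- A man switched to TURP has, on the plan's own figures, the same expected IPSS (4 ± 4), so a shift of 8 points is not the natural assumption for him. Keeping him as allocated can even favour BipolEP, as step 4 shows.

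None of this supplies the missing rule. The never-operated man stays outside ITT on any reading, and no sentence says that men are analysed as allocated.

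**Conclusion.** The point holds as a defect of definition. The set labelled ITT is a treated set, and no planned population contains all allocated men in their allocated arms. The exclusion of men with no operation is explicit; for switched men the defect is that the rule is ambiguous.

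The size cannot be derived from the documents. Under the assumed one-sided loss of 2 to 6 of 34 men scoring 8 points worse, 0.5 to 1.4 points would be hidden. Loss unrelated to outcome hides nothing. It should not be concluded that the bias must favour BipolEP: that holds only if the men lost are poor-outcome BipolEP men. No effect on g/min has been calculated. Because PP leads and would be unchanged, and because the number of men exposed may be small, this is a should-fix.

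**What to change.** 1. Define ITT as all allocated patients, analysed in the arm assigned by minimisation, whether or not that operation was started or another was performed.
2. Collect 12-month IPSS on all of them, and apply the existing worst-case replacement to those without one.
3. For g/min, write an explicit exception to the replacement rule for men who had no prostate operation, since the quantity does not exist for them. State that a switched man contributes the value from the operation received, under his allocated arm.
4. Rename the present set a treated set and report it as supportive.
5. List the events that count as drop-out for PP, and keep PP beside the new ITT set. Switched men kept as allocated dilute the contrast, which is anti-conservative for non-inferiority, so neither set suffices alone.

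The cost is a few sentences and the follow-up of a few extra men. The planned 84 inclusions need not change. Some worst-case values may be added to the ITT analysis. The change is best made early, because an IPSS not collected at 12 months cannot be recovered.

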STUDY PROTOCOL:

Bipolar transurethral enucleation (BipolEP) vs bipolar transurethral resection of the prostate: A prospective interventional multi-center randomized controlled trial

Apporved by the Salzburgs ethics committee on 13.12.2017 Approval Number: 415-E/2251/11-2017

Applicant/	[name]
Coordinating	Uniklinikum Salzburg, University Clinic for Urology and Andrology,
investigator	[name]
Title of trial	Bipolar transurethral enucleation (BipolEP) vs bipolar transurethral resection of the prostate: A prospective interventional multi-center randomized controlled trial
Medical condition	Lower urinary tract symptoms due to benign prostatic enlargement
Objective(s)	The primary objectives of this study is (i) to demonstrate that the I-PSS at 12 months shows non inferiority for enucleation. Our hypothesis is that enucleation and bipolar TURP might be comparable in improving LUTS. The secondary objectives is to show increased tissue resection per minute for the enucleation (superiority) (ii).
Intervention(s)	Experimental intervention: Bipolar transurethral enucleation of the prostate (BipolEP) Control intervention: Bipolar transurethral resection of the prostate (TURP) Follow-up per patient: Dysuria visual analogue scale (at 1 month) I-PSS, QOL, Qmax and PVR (at 1, 4 and 12 months) IIEF-15 and PSA (at 4 and 12 months) TRUS for prostate size at 4 months
Key inclusion and exclusion criteria	Age greater than 50 years Refractory LUTS secondary to BPH I-PSS greater than 15 QOL score 3 or greater Qmax less than 15 ml per second or patients with acute urinary retention secondary to BPH in whom trial of voiding failed Prostate size on preoperative TRUS of 40 to 150 ml Key exclusion criteria: Patients with neurological disorder Active urinary tract infection, active bladder or prostate cancer
Outcome(s)	Primary efficacy endpoints: • IPSS improvement at 12 months Key secondary endpoint(s): • Tissue resection per minute Assessment of safety: • Assessment of possible adverse events after applying BipoLEP and compare to TURP (e.g. bladder perforation, urethra stricture, incontinence). • Comparison of peri- and postoperative complications according to the classification of Clavien-Dindo

	Blood loss (hemoglobin prior and postoperative)
Trial type	Prospective, interventional, multi-centre, randomized trial
	Concept

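### The per-protocol set leads for every variable, safety included, so the leading harm comparison omits every man with a drop-out situation

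*Combined protocol and SAP*

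**What the plan says.** All references are to the combined protocol and SAP.

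- **Analysis Populations, ITT:** "All subjects at whom the group-specific treatment (TURP, BipoIEP) at least has started will be included in the ITT population". All variables are to be analysed in this set.
- **Analysis Populations, PP:** "All subjects without occurrence of any drop-out situation (all valid cases) will be included in the PP population. All variables will be analysed". The next sentence reads: "The PP analysis is paramount". Nothing here limits PP priority to the primary endpoints or to efficacy.
- **Outcome(s), Assessment of safety:** adverse events are to be compared between the arms, with bladder perforation, urethral stricture and incontinence as examples. A second item is "Comparison of peri- and postoperative complications according to the classification of Clavien-Dindo". Blood loss, from hemoglobin before and after surgery, is listed with them.
- **Statistical Methods, Further Variables:** "All other variables will be analysed by usual parametric and non-parametric tests for univariate comparisons of independent samples". Safety variables fall here.
- **Handling of Implausible Values and of Missing Values:** replacement applies only in ITT and only to the two primary endpoints, so no safety value is replaced.
- **Sample Size Justification:** 42 men per group, with 20% drop-out assumed.

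The plan names no safety population, does not exempt safety from PP priority, and does not define a drop-out situation.

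**The concern.** A PP lead can be defended for the IPSS non-inferiority test, because protocol deviations and missing data in an ITT analysis may blur a real difference between the techniques. That argument does not carry over to harms. There, whether a man stays in the set may depend on the outcome being counted: an operation abandoned after a perforation, or follow-up ended because of incontinence, could be classed as a drop-out situation.

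The exclusion also discards data already in hand. Perforation, early Clavien-Dindo events and postoperative hemoglobin are observed around surgery. A man who later has no 12-month IPSS has contributed all of these, yet the PP rule takes them out of the leading comparison.

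At stake is the credibility of the safety comparison. Section 1.2 (The need for a trial) justifies the study by the lack of a randomized comparison of this new device with TURP, so its complication rates will be read closely. If PP and ITT disagree on harms, the plan directs the reader to the set from which some affected men may have been removed.

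**Working it through.** **1. Reproducing the plan's own figure.** Inputs from Sample Size Justification: margin 3, SD 4, true difference 0, one-sided alpha 5%, power 90%, ratio 1:1.

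n per group = 2 × SD² × (1.645 + 1.282)² / margin² = 2 × 16 × 8.57 / 9 = 30.5, rounded up to 31. This matches the plan. Noncentral-t power at 31 per group is 89.9%.

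Drop-out: 31 / 0.8 = 38.75, so 39. The step from 39 to 42 is the allowance for a non-parametric test, whose size is not stated. Nothing in this point changes these figures.

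**2. How many men PP priority can remove.** 42 × 0.20 = 8.4 drop-outs per arm and 42 × 0.80 = 33.6 remaining. Rounded: 8 removed and 34 kept. Over both arms, 84 × 0.20 = 16.8, about 17 men.

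**3. Effect on a complication rate.** The documents give no expected complication rates, so the event counts are assumptions. All 8 drop-outs are taken to occur after the operation started. With E affected men among 42, of whom k are among the 8 drop-outs:

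full rate = E / 42; PP rate = (E − k) / 34.

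| Affected drop-outs (k) | E = 4 (full 9.5%) | E = 5 (full 11.9%) | E = 6 (full 14.3%) |
|---|---|---|---|
| 0 | 4/34 = 11.8% | 5/34 = 14.7% | 6/34 = 17.6% |
| 1 | 3/34 = 8.8% | 4/34 = 11.8% | 5/34 = 14.7% |
| 2 | 2/34 = 5.9% | 3/34 = 8.8% | 4/34 = 11.8% |
| 3 | 1/34 = 2.9% | 2/34 = 5.9% | 3/34 = 8.8% |
| 4 | 0/34 = 0.0% | 1/34 = 2.9% | 2/34 = 5.9% |

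**4. Direction.** The PP rate equals the full rate when drop-outs and completers have the same risk. For E = 5 that is k = 5 × 8/42 = 0.95, about one man. Below that PP overstates the rate; above it PP understates it. At k = 3 the assumed contrast is strong: 3/8 = 37.5% among drop-outs against 2/34 = 5.9% among completers.

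**5. Effect on the comparison.** Suppose both arms truly have 5/42. If one arm loses 3 affected men among its 8 drop-outs and the other loses none, PP shows 5.9% against 14.7%. That is an apparent difference of 3/34 = 8.8 percentage points where there is none.

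**6. Precision.** With zero events, the exact two-sided 95% upper limit is 1 − 0.025^(1/42) = 8.4% for 42 men and 1 − 0.025^(1/34) = 10.3% for 34. This loss is small beside the possible distortion in steps 3 and 5.

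**The case against.** **The ITT analysis also covers all variables.** This stands. A man whose operation started stays in ITT, including one whose operation was abandoned or converted, or who left follow-up because of a complication. A reader might infer that such men vanish from the harm rates altogether; the documents do not support that. They are missing from the leading rates only. The weakness is that the plan ranks the fuller set second.

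**Some men might be in neither set.** A reader might infer this for a man allocated to BipolEP but operated on by TURP from the outset. It needs two readings: that ITT excludes him because his own group's treatment never started, and that the crossover is a drop-out situation. The plan does not state the second. If he completes follow-up, the literal PP wording keeps him in.

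**The bias need not be downward.** This also stands, as the table shows. Understatement requires complications to be more common among drop-outs.

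**The link between complication and drop-out is conjecture.** Partly right. The term is undefined, so the plan does not say that a complication, conversion or re-operation is a drop-out. It does not exclude it either, and any drop-out removes perioperative data already collected, whatever its cause.

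**PP priority over safety is inferred, and safety results are descriptive.** The plan never gives PP priority for safety by name. The reading follows from two general sentences with no exception; if something narrower was meant, one clause would say so. Under Type I error adjustment, results outside hypothesis testing are descriptive only, which limits the stakes, but a descriptive rate from a selectively reduced denominator can still mislead.

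**Conclusion.** The concern holds for the leading safety analysis. Read as written, the plan lets a set conditioned on having no drop-out situation lead the comparison of adverse events, Clavien-Dindo complications and hemoglobin. At the planned 20% this removes about 8 of 42 men per arm. Under the assumed counts, a full rate of 11.9% could appear as anything from 14.7% to 5.9% when 0 to 3 affected men drop out, and the comparison is distorted when this pattern differs between the arms.

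The size depends on assumed event counts, on the drop-outs occurring after surgery has started, and on how drop-out situation is applied. The text does not establish a consistent downward bias, or men who appear in no analysis. Nor does the argument reach beyond safety: it gives no reason to change the lead set for tissue resection or other non-safety variables. The sample size and the IPSS test are unaffected. The point is worth correcting, but the subordinate ITT analysis already gives partial protection.

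**What to change.** In Analysis Populations, state that:

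- the lead analysis of adverse events, Clavien-Dindo complications and hemoglobin uses all men in whom a study operation (BipolEP or TURP) was started, grouped by the operation started, with conversions kept and flagged;
- the sentence "The PP analysis is paramount" does not apply to safety variables;
- PP safety results may be shown as supportive.

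It would also help to define drop-out situation there, so that the difference between the two sets can be read.

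The cost is one short paragraph, with no new data and no change to the 84 inclusions. The small downside is that the stated complication rates may look less favourable. The change does not recover events that occur after a man is lost to follow-up, so the number lost and the time of loss should be reported by arm beside the harm rates.

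### The per-protocol set leads for every variable, so on the plain reading the superiority test on tissue resection (g/min) drops men lost after surgery whose value was already fixed

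*Combined protocol and SAP*

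**What the plan says.** All of this is in the combined protocol and SAP.

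- **PP set (Analysis Populations).** "All subjects without occurrence of any drop-out situation (all valid cases) will be included in the PP population". The text continues: "All variables will be analysed. The PP analysis is paramount". No endpoint is exempted, and the term drop-out situation is not defined.
- **ITT set (same section).** Men in whom the group-specific treatment "at least has started will be included in the ITT population". All variables are analysed here too, but this set does not lead. The wording does not say in which arm a man who received the other procedure is counted.
- **Endpoint 2 (Statistical analysis, Concept).** The plan tests "primary endpoint (2) by a superiority approach (type I error = 2.5% one-sided"), and only if the non-inferiority null hypothesis on 12-month IPSS has been rejected.
- **Follow-up (Intervention(s)).** "I-PSS, QOL, Qmax and PVR (at 1, 4 and 12 months").
- **Drop-out (Sample Size Justification).** "Assuming a drop-out rate of 20"%, the plan arrives at 84 inclusions, 42 per group.
- **Missing data (Handling of Implausible Values and of Missing Values).** "Missing Values will be replaced only in the ITT population and only for the two primary endpoints". The replacement is the worst value assessed in the study.

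**The concern.** A single rule on the leading population covers two endpoints that differ in kind. Endpoint 1 is measured at 12 months and tested for non-inferiority, and leading with PP there is a recognised choice. Endpoint 2 is a rate of the procedure itself and is tested for superiority. Loss to follow-up cannot make a g/min value missing once the operation is over.

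Applying the PP rule to endpoint 2 therefore excludes men because of an event that comes after randomisation and after the outcome is known. This gives up complete data. It also allows selection if the men lost differ in g/min from those who stay and this happens unequally in the two arms.

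Endpoint 2 is the only superiority hypothesis in the gated sequence. If the PP and all-treated results for g/min disagreed, the plan would let PP decide.

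**Working it through.** **Inputs from the documents.** Planned total 84 (42 per group), drop-out 20%, one-sided error 2.5% for endpoint 2. For endpoint 1: margin 3, SD 4, true difference 0, one-sided error 5%, power 90%.

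**Assumptions.** The documents give no effect size or SD for endpoint 2 and no timing of drop-out. Standardised differences of 0.5, 0.7 and 1.0 SD, three timings of drop-out, and the selection effects in step 4 are assumed in order to show a range. That g/min is fixed at the operation is inferred from its unit.

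**1. The plan's own figure.** For endpoint 1, n per group = 2 × (1.645 + 1.282)² × 4² / 3² = 30.4, rounded up to 31, as stated. Allowing for drop-out, 31 / 0.80 = 38.75, or 39 per group. With an assumed efficiency of 0.955 for a non-parametric test, 38.75 / 0.955 = 40.6, or 41, against 42 planned. The sample size is not in dispute.

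**2. Men in the leading endpoint 2 test.**

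- PP: 84 × 0.80 = 67.2, about 67 (33 and 34 per arm).
- All treated, all drop-out after surgery: 84. The standard error ratio is √(1/33 + 1/34) / √(2/42) = 0.2444 / 0.2182 = 1.12.
- All treated, half the drop-out before surgery: 84 × 0.90 = 75.6, about 76. The ratio is √(37.8 / 33.6) = 1.06.
- All treated, all drop-out before surgery: 67, the same men as PP. The ratio is 1.

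**3. Power for endpoint 2 taken alone** (t-test, noncentral t, 2.5% one-sided):

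| Assumed difference | PP, 33/34 | All treated, 38/38 | All treated, 42/42 |
|---|---|---|---|
| 0.5 SD | 52.2% | 57.6% | 62.0% |
| 0.7 SD | 80.6% | 85.3% | 88.7% |
| 1.0 SD | 98.1% | 99.0% | 99.5% |

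The largest loss in the table is 62.0 − 52.2 = 9.8 points. At 1.0 SD the largest loss is 99.5 − 98.1 = 1.4 points.

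**4. Possible selection.** Suppose there is no true difference among all treated men, and the men lost in one arm only differ from that arm's completers by x SD in g/min. The PP difference then shifts by (share of operated men lost) × x. The standard error at 33.6 per arm is √(2/33.6) = 0.244 SD. The rejection rate is that of the one-sided t-test with noncentrality shift / 0.244.

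| Timing of drop-out | Share lost after surgery | x | Shift | Error rate if shift favours BipolEP | Error rate if against |
|---|---|---|---|---|---|
| All after surgery | 0.20 | 0.25 SD | 0.05 SD | 3.9% | 1.5% |
| All after surgery | 0.20 | 0.5 SD | 0.10 SD | 6.0% | 0.9% |
| Half after surgery | 0.10 / 0.90 = 1/9 | 0.25 SD | 0.028 SD | 3.2% | 1.9% |
| Half after surgery | 1/9 | 0.5 SD | 0.056 SD | 4.1% | 1.4% |

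If loss is unrelated to g/min, or selection is the same in both arms, the shift is nil and only precision is lost.

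**The case against.** - **Reading.** The loss depends on an undefined term. The parenthesis about valid cases could mean valid for the endpoint being analysed, which would keep every man with a recorded g/min. A drop-out situation could also mean an event during the operation. This stands as an ambiguity. However, the sentence defines one set of subjects free of any such situation, which reads more naturally per man than per endpoint. Leaving it open would allow the population to be settled after the data are seen.
- **An all-treated analysis is already planned.** True: men lost after surgery keep their observed g/min there, and a discordant result would be visible. Only the ranking of the two analyses is at issue, but the ranking decides the claim.
- **PP brings some gain.** It keeps both steps of the gate in one population, and it may exclude men who did not receive the assigned technique. These gains are small, and they do not justify removing men for later loss to follow-up.
- **Size.** The effect sizes are assumed, 20% after surgery is the upper bound, and nothing in the documents links loss to g/min. All of this stands. The power figures also ignore the gate, so they are not the chance of a formal endpoint 2 claim.
- **Status of the endpoint.** Objective(s) and Outcome(s) call tissue resection secondary, while the Statistical analysis section calls it primary. Under either label it carries a formal gated test, so the point is unchanged.

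**Conclusion.** The point holds. As written, the PP rule governs the g/min superiority test and, on the plain reading, removes up to about 17 of 84 men (84 × 0.20 = 16.8) whose outcome is already complete. The cost in power runs from nothing to about 10 points, depending on when drop-out occurs and on the true difference. Bias is possible but not shown: under one-arm selection of 0.25 to 0.5 SD, the nominal 2.5% error could lie anywhere from 0.9% to 6.0%.

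The conclusion rests on reading the PP definition per subject and on g/min being fixed at the operation. The change should be made. Confidence is medium because of the undefined term.

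**What to change.** Keep PP as the leading analysis for endpoint 1. For endpoint 2, add to Analysis Populations:

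> The primary analysis of tissue resection includes all randomised men in whom surgery started, in the arm to which they were randomised, regardless of later follow-up; the PP analysis is supportive.

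Define drop-out situation, and say whether validity is judged per man or per endpoint. The added sentence also settles the arm in which a man who received the other procedure is counted, which the ITT wording leaves open.

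The cost is SAP wording only. No data are added, the sample size stays the same, and the endpoint 1 test, its power and the gate are unchanged. One consequence should be acknowledged: worst-value replacement would then enter the leading endpoint 2 analysis, but only for operated men whose g/min is missing or was set to missing as implausible. Loss to follow-up does not create such cases.
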